10.0 CRITERIA FOR EVALUATION AND ENDPOINT ANALYSIS

10.1 Complete Response

Complete Response: Negative biopsy for high grade disease at Week 25 (\pm 7 days) for the subset of patients with a CIS component at study entry, according to local pathology call. In addition, patients with a CIS component who undergo negative biopsy at Week 13 for suspicious cystoscopy and or positive cytology and have cystoscopy not suspicious for cancer and cytology not positive for malignant cells at Week 25 do not require repeat biopsy at Week 25 and will be considered to have a complete response at Week 13 and will also be counted as having a complete response at Week 25.

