11.0 STATISTICAL CONSIDERATIONS

11.1 Patient Populations

Eligible patients are defined as registered patients who met all the pre-registration eligibility criteria listed in Section 5 that were in effect at the time of the 12/14/18 amendment. The determination of eligibility regarding Disease Related Criteria will be based on local pathology review.

Evaluable patients are defined as registered patients who received any amount of study drug (atezolizumab).

Efficacy analyses will be based on patients who are determined to be both eligible and evaluable as defined above.

Safety analyses will be based on patients who are determined to be evaluable as defined above. Patients who are registered in the study but who do not receive any study drug will not be included in safety analyses.

11.2 Estimate of Sample Size:

A sample size of 135 eligible patients (evaluable) will be enrolled over 36 months with 18 months of additional follow-up. Our goal is to enroll 70 patients with a CIS component and 65 patients with Ta or T1 disease only. One stratum may be closed prior to accrual completion to ensure adequate patient numbers in both disease groups. An additional 50% will be enrolled to account for ineligibility or initial treatment refusal resulting in a total sample size of 202. With Revision #5 (Version Date 12/14/18) a pre-registration Study Chair approval form was enacted which has significantly reduced the rate of ineligible registrations.

11.3 Analysis:

There will be two co-primary aims for this study: The first objective to be tested involves the complete response rate in the subset of patients with CIS (see [Section 10.1](#)). The second co-primary objective involves event-free survival at 18 months for all evaluable patients. A hierarchical approach will be used to test the two co-primary aims. The CIS aim will be tested first. Only if the result is statistically significant will the second primary objective be evaluated. Only patients who received at least one dose of atezolizumab per protocol will be evaluable for these two primary objectives. Both co-primary tests will be conducted at the one-sided 0.05 significance level.

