The first primary objective is the estimation of the CR rate in the subset of patients with CIS. Enrollment of 70 eligible and evaluable patients with a CIS component will be ensured. If the total number of patients out of 70 who respond is 28 (40%) or greater, the agent would be considered promising. This design has a significance level (probability of falsely declaring that an agent with a 30% complete response probability is worthy of further investigation) of 4.6%, and a power (probability of correctly declaring than an agent with a complete response rate of 50% is worthy of further investigation) of 96%. Seventy evaluable patients are sufficient to estimate the CR rate at 25 weeks (± 1 week) to within $\pm 12\%$ (95% confidence interval). Those CIS patients without a biopsy at 25 weeks will be assumed to be non-responders. Duration of CR is defined as the time from date of biopsy documenting the complete response to the time of first high-grade recurrence, and is a key additional secondary endpoint. With a CR rate of 50%, we would expect 35 patients would have a CR. We can estimate the proportion still in CR at 18 months to within $\pm 17\%$ (95% confidence interval).

One interim futility assessment will be made in the CIS subset. We will evaluate the first 25 eligible and evaluable CIS patients for pathologic response at 25 weeks. Since accrual is expected to be slow, accrual will continue while the interim evaluation is underway. A favorable evaluation would be if 7 or more CRs are seen in the first 25 eligible and evaluable CIS patients. This is equivalent to testing the alternative hypothesis of a 50% complete response rate at the one-sided $\alpha=0.02$. If results are favorable, accrual will continue to a total of 70 eligible and evaluable CIS patients.

The second primary endpoint is event-free survival (EFS) (as defined in [Section 10.0](#)) at 18 months in the mixed population of patients with either CIS or Ta or T1 disease. This objective will only be tested if the null hypothesis in the first co-primary objective is rejected as specified above. The 18-month EFS estimate will be obtained using the method of Kaplan and Meier, and the Greenwood formula will be used to estimate the variance. A 90% confidence interval will be estimated for the 18-month EFS estimate. If the lower 90% confidence bound excludes 20%, the investigators will conclude the regimen significantly improves EFS relative to historical trial data.

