A secondary aim of interest is the assessment of EFS in the Ta/T1 subset. With n=65 eligible and evaluable patients, there will be 71% power to detect Ho: 20% vs. Ha: 30%, using a one-sided alpha=0.05. Other secondary estimates and confidence intervals of endpoints of progression-free survival (PFS), cystectomy-free survival, bladder cancer specific survival (CSS) and overall survival (OS) will also be provided using Kaplan-Meier estimation. Short-term estimates at 18 months and long-term estimates at 5 years for these secondary endpoints will be of interest. Qualitative and quantitative toxicity assessment will be provided using CTCAE reporting. CR and adverse event rates can be estimated to within $\pm 9\%$ (95% confidence interval). A toxicity with a true incidence of 1% (5%) has a 69% (99%) chance of being observed at least once in this single arm trial.

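### Section 11.3 gives ±9% precision for the CR rate when its 70 CIS patients give about ±12%, and a 69% chance of seeing a 1% toxicity when at least 135 treated patients give at least 74%

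*Combined protocol and SAP*

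**What the plan says.** Section 10.1 defines CR "for the subset of patients with a CIS component at study entry"; patients with Ta/T1 disease only have no CR endpoint. The first co-primary paragraph of section 11.3 fixes that subset at 70 and says "Seventy evaluable patients are sufficient to estimate the CR rate at 25 weeks" to ±12% (95% confidence interval).

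Later in section 11.3, after the secondary endpoints, the plan says "CR and adverse event rates can be estimated to within" ±9% (95% confidence interval), and then: "A toxicity with a true incidence of 1% (5%) has a 69% (99%) chance of being observed at least once". No sample size is attached to either statement.

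On the safety denominator, section 11.1 counts a patient as evaluable once any atezolizumab has been given, and says "Safety analyses will be based on patients who are determined to be evaluable as defined above". Eligibility is not required. Section 11.2 says "A sample size of 135 eligible patients (evaluable) will be enrolled over 36 months", and "An additional 50% will be enrolled to account for ineligibility or initial treatment refusal resulting in a total sample size of 202".

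Section 11.5 assumes that 85% of eligible patients yield usable samples, which it works out as 60 CIS patients and 115 patients overall. The EFS-marker power is then given for 115, but the CR-marker power is given for 70, in both the immunohistochemistry and the RNA-sequencing paragraphs.

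**The concern.** Section 11.3 gives two precisions, ±12% and ±9%, for one endpoint in one group of patients, and both cannot hold. The ±9% makes the estimate for the first co-primary objective look about 3 percentage points tighter than 70 patients allow, and someone quoting that paragraph would carry the wrong figure forward.

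The 69% does not match any safety denominator that sections 11.1 and 11.2 allow. It understates the trial's ability to reveal a rare toxicity.

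In section 11.5 a reader cannot tell whether the printed log odds ratios belong to 60 or 70 CIS patients.

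**Working it through.** **Inputs.** CIS patients: 70 (section 11.3). CR rates: 30% null, 50% alternative (section 11.3). Eligible and treated patients: 135; registrations: 202 (section 11.2). Safety set: everyone treated (section 11.1). Usable samples: 60 CIS, 115 overall (section 11.5).

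**1. Precision of the CR rate.** Wald half-width = 1.96 × √(p(1−p)/n).

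The plan's ±12% reproduces: 1.96 × √(0.25/70) = 0.117.

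| CR rate, n = 70 | Wald | Exact (Clopper-Pearson) |
|---|---|---|
| 30% (21/70) | 10.7% | 11.3% |
| 40% (28/70) | 11.5% | 12.0% |
| 50% (35/70) | 11.7% | 12.2% |

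The ±9% does not reproduce for CR. A worst-case half-width of 9% needs n ≥ (1.96 × 0.5/0.09)² = 118.6, so 119 patients. With 70 patients, ±9% holds only if the CR rate is about 18% or less, or 82% or more, outside the two design rates.

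For adverse events the ±9% is sound: at n = 135 the worst-case half-width is 1.96 × √(0.25/135) = 8.4% (exact 8.7%).

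**2. Chance of seeing a toxicity at least once.** This is 1 − (1−p)^n.

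| n | p = 1% | p = 5% |
|---|---|---|
| 115 | 68.5% | 99.7% |
| 118 | 69.5% | 99.8% |
| 135 | 74.3% | 99.9% |
| 202 | 86.9% | more than 99.9% |

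The 1% column rounds to 69% only for n = 115, 116, 117 or 118. Truncating instead of rounding would also admit 119 (69.76%). The planned safety set has at least 135 patients and cannot exceed 202, so the chance lies between 74.3% and 86.9%.

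The only 115 in the plan is the count of patients with usable samples in section 11.5. That may be where the 69% came from, but the plan does not say so.

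**3. Section 11.5.** 0.85 × 70 = 59.5, so 60; 0.85 × 135 = 114.75, so 115. The EFS text uses the reduced number and the CR text does not. The table gives power for the printed CR log odds ratios, with a baseline CR rate of 30% and two-sided α = 0.05.

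| Marker prevalence (log OR) | Pooled z, n = 60 | Wald, n = 60 | Fisher, n = 60 | Continuity-corrected z, n = 60 |
|---|---|---|---|---|
| 25% (1.75) | 82.2% | 76.0% | 75.6% | 72.4% |
| 35% (1.59) | 82.0% | 77.8% | 76.2% | 73.3% |
| 45% (1.52) | 81.5% | 78.0% | 77.7% | 73.2% |

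The pooled z-test at n = 115 reproduces the printed EFS log odds ratios (1.280, 1.186, 1.152 against 1.28, 1.19, 1.15). With the same test, the printed CR values reach 80% power at about 57 to 58 patients, not 70. With the continuity-corrected test they fit about 68 to 69 patients, but that test does not reproduce the EFS figures (1.378, 1.269, 1.228).

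**The case against.** The correct CR precision is already in the plan, tied explicitly to 70 patients in the paragraph on the co-primary objective, and a reader of section 11.3 meets it first. The later paragraph concerns secondary endpoints and toxicity, its ±9% is valid for adverse events, and the defect comes down to the one abbreviation CR. This is a fair account of the weight of the error, but the sentence as written is still false for CR.

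The 69% errs on the cautious side, the 99% for a 5% toxicity is true as a floor, and no stopping or monitoring rule uses either number. All of that stands, and it limits the consequence without making 69% right.

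The section 11.5 point is the weakest. The analyses are exploratory. The test is named there (logistic regression, with Fisher's exact test as a fallback), and only the power formula is missing. Under the pooled z-test that fits the EFS figures, power exceeds 80% at either 60 or 70. So a shortfall in power is not shown. What remains is that the printed 70 contradicts the 60 assumed in the same section.

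**Conclusion.** The point holds. The ±9% for CR is wrong and contradicts the ±12% in the same section. With 70 patients the half-width is 10.7% to 12.2% across CR rates of 30% to 50%, depending on the rate and the interval method. The 69% is too low by at least 5 points: 74.3% at 135 treated patients, and at most 86.9% if all 202 registered patients were treated. This assumes that the planned 135 eligible and treated patients are reached and that patients experience the toxicity independently with the stated probability.

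The conflict between 60 and 70 in section 11.5 is one of labelling. Loss of power is possible under some tests but not established.

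The matter is minor. The 28-of-70 rule, the interim rule of 7 of 25, the EFS test, the sample size and data collection are unaffected.

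**What to change.** In section 11.3, delete CR from the ±9% sentence, or give CR its own figure of ±12% with n = 70. Keep ±9% for adverse event rates and attach n = 135. Restate the detection figures as at least 74% (more than 99%) for a toxicity of 1% (5%) incidence with at least 135 treated patients.

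In section 11.5, state 60 CIS patients for the CR markers in both the immunohistochemistry and RNA-sequencing paragraphs, name the formula or test behind the power figures, and recompute the power or the detectable log odds ratios with it.

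The cost is a few words and one short power calculation.

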11.4 Estimate of Accrual Rate

Target accrual will be 4 patients per month with planned completion of the accrual in 36 months.

11.5 Statistical Plan for Translational Aims

For all analyses in this study, the investigators will consider the use of non-parametric or robust alternatives in the case when distributional assumptions or asymptotic approximations fail. Further, for simplicity, complete follow-up will be assumed on all

patients, but alternative statistical approaches accommodating censoring and potential confounders (e.g. technical batch) will be used if necessary. It will also be assumed that 85% of eligible patients (60 eligible CIS patients and 115 eligible patients in total) will have usable samples for the specified assessment.

Immunohistochemistry (Objective 1.3.b): To assess the association between PD-L1, as quantified via IHC, a dichotomous indicator of positive PD-L1 expression will be created for each patient sample: if $\geq 5\%$ of cells express PD-L1, then the sample will be scored as positive; otherwise, the sample will be negative. Logistic regression will then be used to regress the dichotomous CR status of each CIS patient on the indicator of PD-L1 expression. Fisher's exact test may be used if the proportion of complete responders or proportion of patients expressing PD-L1 is small. Similarly, using all patients, logistic regression will also be used to regress dichotomous 18-month EFS status of each patient on the indicator PD-L1 expression. The analysis will be repeated with CD8 expression as well as other markers. The type I error rate will be controlled at the two-sided $\alpha=0.05$.

For the CR endpoint in CIS patients, assuming baseline CR rate of 30%, then with a sample size of 70, 80% power is anticipated to detect a log odds-ratio of 1.75, 1.59, and 1.52, if the particular marker is positive in 25%, 35%, or 45% of the CIS patients, respectively. For the 18-month EFS endpoint, assuming a baseline 18-month EFS rate of 20%, then with a sample size of 115 patients, investigators anticipate 80% power to detect a log odds-ratio of 1.28, 1.19, and 1.15 if a particular marker is positive in 25%, 35% or 45% of the patients, respectively.

RNA sequencing (Objective 1.3.b): Following preprocessing and normalization of the RNAseq data, it will be determined whether each patient expresses the pre-defined signature. Then to determine whether pre-defined signatures are predictive of complete response in CIS patients, logistic regression will be used to regress CR status for each CIS patient on an indicator for whether each patient expresses the signature. Similarly, to determine whether pre-defined signatures are predictive of 18-month EFS in all patients, logistic regression will be used to regress 18-month EFS status for each patient on an indicator for whether each patient expresses the signature. This analysis will be repeated for each signature considered. Investigators will again consider using Fisher's exact test if the CR or 18-month EFS rates or the proportion of patients expressing the signature are low. Type I error rate will be controlled at the 2-sided $\alpha=0.05$ level.

For the CR endpoint in CIS patients, assuming baseline CR rate of 30%, then with a sample size of 70, 80% power is anticipated to detect a log odds-ratio of 1.75, 1.59, and 1.52, if the percentage of CIS patients expressing the signature is 25%, 35%, or 45%, respectively. For the 18-month EFS endpoint in all patients, assuming a baseline 18-month EFS rate of 20% for patients not expressing the signature, then with 115 patients, investigators anticipate 80% power to detect a log odds-ratio of 1.28, 1.19, and 1.15 if the percentage of patients expressing the signature is 25%, 35% or 45%, respectively.

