1.3 Additional Objective(s)

- a. To estimate the level of agreement between local and central pathology review in terms of recurrence (for all patients) and complete response (for the CIS subset).
- b. To identify markers that predict response to atezolizumab in the CIS population and that are associated with EFS in patients with Ta/T1/CIS BCG-unresponsive non-muscle invasive bladder cancer. The following markers will be tested:
 - Expression of PD-L1 and CD8 by immunohistochemistry (IHC)
 - Expression of immune signatures by RNA-sequencing (RNA-seq)
 - Peripheral immune response by mass cytometry (CyTOF) and TruCulture

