6.0 STRATIFICATION FACTORS

CIS: Present vs. Absent (i.e., Ta/T1 only)

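### The marker-EFS analyses use unadjusted logistic regression of 18-month status; a Cox model stratified by CIS should be pre-specified, with its power gain stated as conditional

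*Combined protocol and SAP*

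**What the plan says.** Section 1.3 (objective b) seeks markers "that are associated with EFS in patients with Ta/T1/CIS BCG-unresponsive non-muscle invasive bladder cancer", with no restriction to 18 months. Section 11.5 turns this into a binary analysis. For PD-L1, and then CD8 and other markers, "logistic regression will also be used to regress dichotomous 18-month EFS status" on the marker indicator. For each RNA-seq signature, "logistic regression will be used to regress 18-month EFS status for each patient on an indicator for whether each patient expresses the signature". Neither model contains another term.

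On missing follow-up, Section 11.5 states that "for simplicity, complete follow-up will be assumed on all" patients. The same sentence allows other approaches for censoring and confounders where needed, with technical batch as its one example. It names no method and no trigger.

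Elsewhere, Section 10.7 defines EFS as a time from registration, censored at last contact, and Section 11.3 analyses it by Kaplan-Meier. Section 6.0 lists one stratification factor, CIS present or absent. Section 7.7 follows all patients for 5 years.

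**The concern.** Two things are lost.

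- **Stratum.** The model pools two disease groups that differ at entry and in how events are found. Under Section 5.2, visible tumour must be resected completely, but CIS is not expected to be. Under Section 7.3, CIS patients have a mandatory Week 25 biopsy (with one stated exception), while Ta/T1 patients are biopsied only for suspicious findings. If a marker is also more common in one group, its crude association with EFS mixes the marker effect with the CIS effect.
- **Time.** The binary outcome discards event times and everything after 18 months. It also needs a known 18-month status for every patient, which the plan supplies by assumption.

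At stake is whether a reported marker-EFS association, or its absence, can be read as belonging to the marker. Several markers and signatures are to be tested, so leaving the model open until the data are seen also invites selective choice.

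**Working it through.** **Inputs.** From Section 11.5: n = 115, 20% EFS at 18 months in marker-negative patients, two-sided 0.05, and log odds-ratios 1.28, 1.19 and 1.15 at marker prevalence 25%, 35% and 45%. From Section 11.2: 36 months of accrual plus 18 months, hence 18-54 months of follow-up per patient. About 60 of the 115 usable samples come from CIS patients, leaving 55 Ta/T1. Dropout, hazard shape, CIS effect and marker prevalence by stratum are assumptions, because the documents give none.

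**1. The plan's own figure.** At 35% prevalence, the marker-positive odds are 0.25 × e^1.19 = 0.822, so the rate is 0.822/1.822 = 45.1%. With 40.25 positive and 74.75 negative patients, the pooled rate is 28.8%, the null standard error 0.0885 and the alternative standard error 0.0911. Power = Φ[(0.251 − 1.96 × 0.0885)/0.0911] = Φ(0.85) = 80.3%. The other two prevalences give 80.0% and 79.9%. The stated 80% is reproduced.

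**2. The same effects as hazard ratios.** Under proportional hazards, HR = ln(p1)/ln(0.20), where p1 is the marker-positive rate. This gives 0.465, 0.495 and 0.508. At 35% prevalence, events by 18 months are 74.75 × 0.80 + 40.25 × 0.549 = 81.9. Schoenfeld power is Φ[√(81.9 × 0.35 × 0.65) × |ln 0.495| − 1.96] = 86%. Simulation on the protocol's visit schedule gives less, and is used below.

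**3. Simulated power** (%, 3,000 trials per scenario; ranges run over the three prevalences; Cox is the CIS-stratified score test):

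| Assumption | Logistic | Cox, cut at 18 months | Cox, 18-54 months |
|---|---|---|---|
| Proportional hazards | 79-80 | 79-81 | 87-89 |
| Same, 10% dropout by 18 months | 76 | 76-80 | 85-87 |
| Same, CIS log HR 0.7 | 72-75 | 78-81 | 86-89 |
| Marker effect ends at 18 months | 78-81 | 77-82 | 69-74 |
| Whole effect before Week 25 | 82-83 | 87-89 | 77-82 |
| Effect only after Week 25 | 74-76 | 57-62 | 85-88 |

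With 10% dropout, about 6% of patients have no known 18-month status. A separate simulation gave 88-90% for Cox over 18-54 months under proportional hazards, and 67-73% when the effect ends at 18 months. Type I error was about 5% for all tests when CIS did not confound.

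**4. Confounding by CIS, with no true marker effect.**

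- *Larger contrast:* prevalence 50% in CIS and 20% in Ta/T1; EFS 12% and 29%. Marker-positive: 30 CIS and 11 Ta/T1, (30 × 0.12 + 11 × 0.29)/41 = 16.6%. Marker-negative: 30 and 44, (30 × 0.12 + 44 × 0.29)/74 = 22.1%. Crude odds ratio = (0.166/0.834)/(0.221/0.779) = 0.70.
- *Smaller contrast:* prevalence 45% and 25%; EFS 15% and 26%. The rates are 18.7% and 21.1%, and the crude odds ratio is 0.86.

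In these examples the unadjusted test rejects a true null 6-12% of the time. A wider set of assumed contrasts gave 7-17%, against 5% for the stratified test. With a true log odds-ratio of 1.19 opposing the confounding, unadjusted power in the examples is 44-66% instead of the stated 80%. Adjustment would not recover all of that, because marker and CIS are then correlated.

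**The case against.** The strongest defence has four parts.

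- **The plan has an escape clause.** A reader might infer that it makes no provision for censoring or confounding. That is not so: Section 11.5 allows alternatives, and its batch example does not exclude CIS. What stands against it is that method and trigger are unspecified and CIS is not named.
- **18-month status fits the trial.** It is the co-primary landmark, Section 7.3 requires CT or MRI at Week 73 in patients free of high-grade recurrence, and the co-primary EFS analysis is not stratified by CIS either. This is a good reason to keep an 18-month analysis. However, the co-primary analysis estimates one rate in the whole group, so confounding between patients does not arise there; in a marker comparison it does.
- **More power is not assured.** A reader might infer that Cox is simply the more powerful test. The table in the working contradicts that. Treatment stops after at most 17 cycles (51 weeks), so a waning effect is possible. The historical table in Section 11.3 also flattens: gemcitabine goes from 28% at 12 months to 20% at 24, where a constant hazard would give 0.28² = 8%. With such flatter shapes, still under proportional hazards, Cox over 18-54 months has about 85-89%. This objection stands and limits the claim.
- **The confounding is assumed and modest.** A spurious odds ratio of 0.70-0.86 is small beside the 3.2-3.6 the aim is powered to detect (e^1.15 to e^1.28). The observation is correct, but it does not remove the inflated error rate or the loss of power in those scenarios.

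**Conclusion.** The point holds in limited form. The planned marker-EFS models omit the trial's one stratification factor and reduce a censored time-to-event endpoint to a binary one, when the data for a better analysis are already collected.

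The case for including CIS does not depend on a power gain from Cox. It rests on the possibility that prevalence and EFS both differ by CIS, which the documents neither show nor exclude. A reader might infer that CIS does confound these markers; nothing in the documents establishes that, and the 7-17% error rate describes assumed scenarios only.

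The power case is conditional. It is worth roughly 7-10 points over about 80% if hazards are proportional and follow-up beyond 18 months is used. It is close to nil at an 18-month cut, and it reverses if the effect stops at 18 months. Because this is an additional objective and the stated 80% is correctly calculated, the matter is a desirable improvement, not a threat to the primary conclusions.

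**What to change.** In Section 11.5, for both IHC and RNA-seq:

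1. Name a Cox model for EFS, stratified by CIS (present or absent), as the main marker-EFS analysis, using all follow-up to a stated data cut and censoring as in Section 10.7.
2. Pre-specify a proportional-hazards check and how the result will be reported if it fails.
3. Keep the 18-month logistic model as a sensitivity analysis, with CIS as a covariate and a stated rule for patients whose 18-month status is unknown.
4. Restate the EFS power paragraph in hazard ratios (0.465, 0.495 and 0.508 correspond to the present log odds-ratios), with the proportional-hazards assumption and follow-up made explicit.

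The cost is SAP wording, with no new data, visits or patients. The price is a hazard ratio in place of an odds ratio, and power that depends on roughly proportional hazards.
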